#### 4.6.3 Subgroup Analyses

Subgroup analyses are planned for the change from baseline in PROMIS-PI. An MMRM model will be used to test for treatment by subgroup interactions. Interactions with a significance level of less than 10% will be considered potentially important and flagged for further assessment. In general, the models will include fixed categorical effects for treatment, week, treatment by week interaction, subgroup, and treatment by subgroup interaction. The p-values of interaction terms will be presented, as well as the least squares means and 95% confidence intervals by treatment and subgroup classification factor. Descriptive statistics of the observed and change from baseline PROMIS-PI t-score will also be presented by treatment and week within each subgroup.

Subgroup analyses will be performed for the following subgroups:

- Dosage of VR (minutes per week)
- Previous experience with VR
- ITQ cutoff score
- Presence cutoff score
- Patient comorbidities
- History of spinal surgery
- Pain severity and duration cutoffs
- Socio-demographics (i.e. age, sex, race, ethnicity, marital status, zip code)
- Other Medications
- TAPS-1, TAPS-2

The primary MMRM models will be refit to include terms describing subgroups. The change from baseline PROMIS-PI score obtained for Day 30 will be compared between the treatment groups using MMRM analysis. The repeated measures are the change from baseline PROMIS-PI score obtained for Day 7, 15, 21, and 30, respectively. The model will include fixed categorical effects for treatment, week, treatment by week interaction, relevant subgroup, treatment by subgroup interaction, and the baseline PROMIS-PI score as a continuous covariate. The estimated least squares means and 95% confidence intervals on the treatment comparison for Day 7, 15, 21, and 30 will be presented in forest plots for each subgroup of relevance.

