#### 9.4.7 SUB-GROUP ANALYSES

Subgroup analyses are planned for the change from baseline in PROMIS-PI. An MMRM model will be used to test for treatment by subgroup interactions. Interactions with a significance level of less than 10% will be considered potentially important and flagged for further assessment. In general, the models will include fixed categorical effects for treatment, week, treatment by week interaction, subgroup, and treatment by subgroup interaction. The p-values of interaction terms will be presented, as well as the least squares means and 95% confidence intervals by treatment and subgroup classification factor. Descriptive statistics of the observed and change from baseline PROMIS-PI t-score will also be presented by treatment and week within each subgroup.

Subgroup analyses will be performed for the following subgroups:

- Dosage of VR (minutes per week)
- Previous experience with VR
- ITQ score
- Presence score
- Patient comorbidities
- History of spinal surgery
- Pain severity and duration
- Sociodemographics (i.e. age, sex, race, ethnicity, workers comp, marital status, education)
- Other treatments (see section 6.5)
- TAPS-1, TAPS-2
- Mood disturbances (e.g., current depressive disorder or not, severely depressed mood vs. non-depressed, etc.)
- Radicular vs. non-radicular back pain
- SSQ Cutoff (Score of >15)
- Treatment Expectation Question
- Perception of arm of study question
- Motion Sickness Propensity Survey

The primary MMRM models will be re-fit to include terms describing subgroups. The change from baseline PROMIS-PI score obtained at Day 30 will be compared between the treatment groups using MMRM analysis. The repeated measures are the change from baseline PROMIS-PI score obtained for Day 7, 15, 21, and 30, respectively. The model will include fixed categorical effects for treatment, week, treatment by week interaction, relevant subgroup, treatment by subgroup interaction, and the baseline PROMIS-PI score as a continuous covariate. The estimated least squares means and 95% confidence intervals on the treatment comparison for Day 7, 15, 21, and 30, will be presented in forest plots for each subgroup of relevance.

See Section 9.4.9 under exploratory analysis for more detail.

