
To assess the efficacy of Skills-Based and Distraction VR via patients' global impression of change (PGIC). The objective will be considered achieved if there is statistical evidence of higher rates of self-reported improvement in either VR group compared to control (sham) VR.
	
The overall effect of treatment from study baseline to Day 90 as measured by the PGIC is an exploratory endpoint. This scale measures self-reported belief regarding efficacy of treatment. A favorable response of 5-7 on the PGIC indicates significant improvement occurred over the course of the study. We will test for a statistically significant difference in PGIC responses between either VR group and control (sham) VR.

To assess the efficacy of Skills-Based and Distraction VR in improving measures of physical activity from baseline to Day 90. The objective will be considered achieved if there is statistical evidence of measured improvement in either VR group compared to control (sham) VR.
	
The change from study baseline to Day 90 in weekly steps as measured by Fitbit is an exploratory endpoint. Change in steps will also be examined for interaction effects on the primary outcome.

To assess the effect of presence on the efficacy of Skills-Based and Distraction VR in improving measures of pain interference from baseline to Day 30.
	
The effect of presence - as measured by a custom, 6-item survey - on the efficacy of VR treatment for pain is an exploratory endpoint. Scores on the survey at Day 1 will be examined for interaction effects on the primary outcome.

To assess the effect of Immersive Tendencies on the efficacy of Skills-Based and Distraction VR in improving measures of pain interference from baseline to Day 30.
	
The effect of immersive tendencies - as measured by the ITQ - on the efficacy of VR treatment for pain is an exploratory endpoint. Scores on the ITQ at baseline will be examined for interaction effects on the primary outcome.

To assess the effect of dose on the efficacy of Skills-Based and Distraction VR in improving measures of pain interference from baseline to Day 30.
	
The effect of dose - as measured by minutes spent accessing therapeutic content on the VR device - on the efficacy of VR treatment for pain is an exploratory endpoint. Minutes spent accessing therapeutic content will be examined for interaction effects on the primary outcome.

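### SAP 4.6.3 tests effect modification at cutoffs that are never defined: for ITQ and presence this is out of step with the SAP's own objectives, and for pain severity and duration the cutoffs are absent from the protocol

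*SAP*

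**What the plan says.** SAP 4.6.3 Subgroup Analyses refits the primary MMRM with a subgroup term and a treatment-by-subgroup term, both as fixed categorical effects. Interactions below the 10% level are flagged. The list includes "ITQ cutoff score", "Presence cutoff score" and "Pain severity and duration cutoffs". No cutoff value follows, there or elsewhere in the SAP.

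SAP 3.2 Study Objectives and Endpoints puts the exploratory questions in terms of scores. For immersive tendencies: "Scores on the ITQ at baseline will be examined for interaction effects on the primary outcome". For presence: "Scores on the survey at Day 1 will be examined for interaction effects on the primary outcome". No SAP objective treats pain severity or pain duration as an effect modifier.

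Protocol 9.4.7 lists ITQ and presence as scores and gives the pain item as "Pain severity and duration", with no cutoff. The only numeric cutoff in either subgroup list is the protocol's SSQ score above 15. The protocol shares the SAP's categorical-effects wording and also reports "least squares means and 95% confidence intervals by treatment and subgroup classification factor".

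**The concern.** Someone working from the SAP's objectives would fit a treatment-by-score term. Someone working from its subgroup list would first cut the score at a value nobody has written down. These are different tests and can give different answers.

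Two things are at stake. First, cutting a continuous modifier discards information, and these interactions have no planned power to spare. Second, an open cutoff can be settled after the data are seen. SAP 6.3 places exploratory tests outside the gatekeeping, so nothing else in the plan limits that choice. The matter is not incidental: Protocol 2.2 asks which patient characteristics predict response, and the protocol synopsis names ITQ and presence as tertiary objectives.

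**Working it through.** **Inputs from the documents.** 120 patients per arm (SAP 3.3). SD of PROMIS-PI 10 at each time, so SD of change √(10² + 10²) = 14.14 at zero correlation; 5-point effect; two-sided 0.025 per comparison; stated power 83% (SAP 3.5). Interaction flag level 10% (SAP 4.6.3). The documents give no distribution for ITQ, presence, pain severity or duration, and no power for any interaction, so the shapes and slopes below are assumptions.

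**The plan's own figure.** Simulating two t-tests against a shared control, with success if either p < 0.025, gives 83.5% against the stated 83%. The plan's inputs reproduce.

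**Information kept after one cut.** For a linear interaction, this is the squared correlation between the score and its group indicator. For a normal score cut so that a fraction p lies on one side, with φ the normal density and z_p the cut point:

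E = φ(z_p)² / [p(1 − p)]

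| Cut of a normal score | Kept | Lost |
|---|---|---|
| 50:50 | 63.7% | 36.3% |
| 1/3 : 2/3 | 59.5% | 40.5% |
| 25:75 | 53.9% | 46.1% |
| 20:80 | 49.0% | 51.0% |

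For one VR arm against sham, n = 240. A median split is then worth 240 × 0.637 ≈ 153 patients and a 25:75 cut 240 × 0.539 ≈ 129.

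**Other shapes and more groups** (between-group share of variance):

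- Uniform score, median split: 25% lost.
- Normal score, tertiles: 21% lost; quartiles: 14% lost.
- Rounded 0–10 scale with assumed mean 6 and SD 2, median split: about 35% lost.
- Exponential score: 52% lost at the median, 35% at the best cut searched.
- Lognormal score (sigma 0.5): 49% lost at the median, 39% at the best cut searched.

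**Power at the 10% level.** Take an assumed effect that changes by 0.3 SD per SD of the score, which is 0.3 × 14.14 = 4.2 points. The standard error of the interaction, in SD units, is 2/√240 = 0.129, so the standardised effect is 0.3/0.129 = 2.32. Power is about Φ(2.32·√E − 1.645):

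- score kept whole (E = 1): 75%;
- median split (E = 0.637): 58%.

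Simulation gives 74% and 57%. At a slope of 0.25 SD the formula gives 62% and 46%.

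More groups do not recover this, because they spend degrees of freedom. Tertiles have noncentrality 2.32² × 0.793 = 4.3 on 2 df, which gives 57%.

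**Effect of a free cutoff.** With no true interaction and the smallest p-value kept across candidate cuts of one score, simulation gives a false-flag rate of about 23% with three candidates (the quartile points) and about 34% with seven (20th to 80th percentiles). The continuous score stays at about 10%.

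**The case against.** The strongest reply is that the protocol does not commit to continuous terms either. It uses the same categorical-effects language and presents results by classification factor, so listing a score beneath that text may only name the variable. The SAP objectives could also be read with grouped scores. This largely stands: the wording is inconsistent, but it is not a flat contradiction between two specified methods.

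A reader might infer that the SAP contradicts its objectives for pain severity and duration as well. The documents do not support that. No SAP objective covers them, and the protocol's entry states neither score nor category. For pain the problem is an undefined cutoff that the protocol list lacks.

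A reader might also infer that a third or more of the information is always lost. That needs a single cut, a bell-shaped or right-skewed score and a linear interaction. The SAP speaks of cutoffs in the plural for pain, and a uniform score or several groups would lose less.

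A cut is also not always the weaker method. Both background sections report greater benefit at pain above 7 on a 0–10 scale. If modification really were a step at the chosen value, a linear term would be the inefficient one. That is a fair point, and it is why a curvature check belongs in the fix.

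Finally, statisticians work with arms coded A, B and C. This limits steering a cutoff towards a known arm, but cutoffs can still be searched on coded arms.

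**Conclusion.** The point holds as a specification gap with a better method available at little cost. Four modifiers are to be cut at values that neither document defines. For two of them, ITQ and presence, the subgroup list is out of step with the SAP's own objectives and the protocol list.

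For a normal score, a linear interaction and one cut, the loss is about 36% of the information at the median and 46% at 25:75. Under the other shapes and groupings tried, it runs from 14% (normal quartiles) to about half (skewed scores cut at the median). The fall from about 74% to 57% in the chance of a flag also depends on an assumed slope of 0.3 SD per SD. At 4.2 points, that slope is close to the whole 5-point target effect and should be read as illustrative.

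It would go too far to infer that the trial's main findings are at risk. These are exploratory analyses whose results are only flagged for further assessment, so the primary and secondary conclusions do not depend on them.

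**What to change.** In SAP 4.6.3 Subgroup Analyses, test the treatment interaction with the continuous ITQ, presence, pain severity and pain duration scores, and add a spline check for curvature or a threshold. Use categories only for forest plots and descriptive tables, at cutoffs written into the SAP before unblinding. Align SAP 3.2 Study Objectives and Endpoints, SAP 4.6.3 and Protocol 9.4.7 so that each names the same form of each variable. If the sponsor prefers to test categories, the cutoffs and number of groups still need to be stated and the sections reconciled.

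The cost is wording only; no new data are needed. The downside is that linearity is assumed unless the spline check shows otherwise.

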## **4.7 Analysis of Safety**

All safety analyses will be descriptive. No statistical testing will be performed.

## **5. CHANGES IN THE CONDUCT OF THE STUDY OR PLANNED ANALYSES**

### **5.1 Detailed Changes in the Conduct of the Study**

For a broad overview, please see the amendment summaries for Protocol 00000631.

*CHANGES WILL BE DETAILED HERE*

### **5.2 Detailed Changes in the Analyses Planned in the Protocol**

For a broad overview, please see the amendment summaries for Protocol 00000631.

*CHANGES WILL BE DETAILED HERE*

## **6. GENERAL STATISTICAL/ANALYTIC ISSUES AND APPROACHES**

### **6.1 Handling of Dropouts or Missing Data**

For randomized patients who discontinue early from the study, measurements will not forward to the date of discontinuation. For purposes of analysis, their last day in the study will be the last day on which data was contributed. Unless stated otherwise on a case-by-case basis, no further imputation will be used for descriptive analyses, or for primary and secondary efficacy analyses utilizing MMRM methodology.

### **6.2 Interim Analyses and Data Monitoring**

No formal interim analysis or interim statistical testing for treatment comparisons is planned.

Response rates and patient safety data will be monitored by an independent DMSB until the last patient completes his last scheduled assessment. The DMSB will be an external group overseeing the safety of the study treatment through an executive secretary (Navitas Life Sciences). The principal investigator(s) will meet with the DSMB on a biannual basis, once via teleconference (approximately 2 hours) and once in-person (approximately 4 hours). Additional meetings may be held ad hoc or routinely, if determined necessary. The research team submits a monthly enrollment report to NIAMS via the Executive Secretary to review enrollment progress and safety monitoring data.

### **6.3 Multiple Comparisons/Multiplicity**

The family-wise type I error rate (FWER) for the statistical tests of the primary and secondary endpoints will be controlled at 0.05. To strongly control the FWER at this level, a gate-keeping approach will be utilized in which each family of statistical tests will be conducted in a sequential manner. A closed testing procedure will be employed to control the FWER. Hypothesis tests conducted for exploratory purposes will be conducted outside of any gatekeeping.

## 6.4 Missing Data and Sensitivity Analyses

If the primary or key secondary endpoint is missing in >15% of patients in either treatment group, then the pattern of baseline covariates with missing values will be examined using the method of Little and in case the data is not missing completely at random, missing values will be imputed using fully conditional specification with the multivariate imputation by chained equations (MICE) algorithm under the missing at random (MAR) assumption. Fifty or so data sets will be generated and analyzed separately, and the results will be combined using the formula according to Van Buuren. Similar considerations will be applied to missing data on the dependent variable in a repeated measure mixed model by investigating patterns of missingness and presence of nonignorable missing response data.

